### **10.1.4 $\geq 75\%$ reduction in 28-days partial-onset seizure frequency**

The analyses described in Section 10.1.3 for  $\geq 50\%$  reduction in 28-days partial-onset seizure frequency will also be performed for study participants with  $\geq 75\%$  reduction in 28-day partial-onset seizure frequency ( $\geq 75\%$  responders).

### **10.1.5 Seizure days per 28 days (subjects with generalized seizures only)**

For study participants with generalized seizures, the number of seizure days per 28 days (as defined in Section 3.2.16) will be summarized descriptively during the treatment period.

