#### **2.3.4.2 Secondary efficacy variables**

The secondary efficacy variables, based on daily seizure diaries are:

- Percent change from Baseline in 28-day partial-onset seizure frequency
- $\geq 50\%$  reduction in 28-day partial-onset seizure frequency
- $\geq 75\%$  reduction in 28-day partial-onset seizure frequency
- Seizure days per 28 days (subjects with generalized seizures only)
- Seizure-free status

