### **3.2.16 Seizure day**

A seizure day is defined as a day where any type of seizure was reported in the seizure diary and seizures were assessed. Days in the seizure diary which are marked as “not done” on the CRF/eCRF will not be counted as a seizure day.

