### 3.2.20 Number and percentage of seizure-free days

The number of seizure-free days will be the total number of days within an interval for which daily diary data was available and no seizures were reported. The percentage of seizure-free days will be computed as 100 times the number of seizure-free days in the interval divided by the number of days in the interval for which daily diary data was available. Days without the corresponding daily diary data will not be used in these computations (ie, days where “not done” is marked on the Seizure Frequency CRF/eCRF module). The change in percentage of seizure-free days will be calculated relative to Baseline (using the Baseline definition in Section 3.3).

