### 10.1 Seizure counts

At Screening of SP847 (or other LCM pediatric clinical studies in epilepsy) or at the Screening Visit of SP848 (for study participants who directly enrolled into SP848) study participants/caregivers (including parents/legal guardians) will be asked how many seizures the subject has had in the previous 4 weeks; this will serve as a historical Baseline. After the subject is enrolled in the SP848 study, seizure data will be collected in diaries provided to study participants/caregivers (including parents/legal guardians). Each subject/caregiver (including parent/legal guardian) will keep a diary to note daily seizure activity throughout the current study. The subject/caregiver (including parent/legal guardian) should be reminded to bring the diary with them at each clinic visit. The following information will be recorded:

- Seizure type
- Seizure frequency

Each seizure code in the clinical database will be mapped to exactly 1 of the ILAE seizure codes based on the 1981 ILAE classification (Seizure Count CRF/eCRF module).

Determination of Baseline Period seizures will be made utilizing both the historical Baseline and the seizure diary data collected from the date of the Screening Visit to the day prior to the date of first dose of LCM.

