### **10.1.1 Seizure frequency per 28 days**

For study participants with POS, seizure frequency per 28 days (as defined in Section 3.2.13) will be summarized descriptively and presented graphically.

Observed values and change from Baseline during the Titration Period, Post-Titration Period and the overall Treatment Period for the direct enrollers, overall Treatment Period for rollover study and overall Treatment Period for all study participants will be presented.

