### **10.1.2 Percent change from Baseline in 28-day partial-onset seizure frequency**

For study participants with POS, descriptive statistics for percent change from Baseline (as defined in Section 3.2.14) in 28-day seizure frequency will be presented. Any subject with seizure data during the time interval will be included in the summary for that seizure time interval.

Descriptive statistics will also be presented for percent change from Baseline in 28-day seizure frequency during the Titration Period, Post-Titration Period and for the overall Treatment Period for direct enrollers, for the overall Treatment Period for the rollover study participants and for the overall Treatment Period for all study participants.

Descriptive statistics for percent change from Baseline in 28-day seizure frequency during the Treatment Period will also be presented by seizure type (simple partial, complex partial, secondarily generalized) for POS. Only study participants who experienced a seizure type during the Baseline Period will be included in the analysis for that seizure type with only the seizure frequencies of that seizure type being used in the analysis.

Descriptive statistics for percent change from Baseline to each time interval in 28-day seizure frequency during the Treatment Period will also be presented. Any subject with seizure data during the time interval will be included in the summary for that seizure time interval and by seizure type.

The percent change from Baseline in 28-day seizure frequency among completer cohorts (as defined in Section 3.2.19) will also be presented.

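### Seizure days per 28 days, the variable reserved for generalized-seizure participants, is planned only as a treatment-period level and so cannot show direction of change

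*SAP*

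**What the plan says.** SAP Section 2.3.4.2 lists five secondary efficacy variables. One is reserved for this subgroup: "Seizure days per 28 days (subjects with generalized seizures only"). Its whole analysis is one sentence in Section 10.1.5: "the number of seizure days per 28 days (as defined in Section 3.2.16) will be summarized descriptively during the treatment period". The section cited there, 3.2.16, defines the unit: "A seizure day is defined as a day where any type of seizure was reported in the seizure diary and seizures were assessed". Neither section mentions Baseline.

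The POS analyses are built differently. Section 10.1.1 opens: "For study participants with POS, seizure frequency per 28 days (as defined in Section 3.2.13) will be summarized descriptively and presented graphically". It then asks for "Observed values and change from Baseline during the Titration Period, Post-Titration Period and the overall Treatment Period for the direct enrollers", and for the whole Treatment Period in rollovers and in all participants. Section 10.1.2 adds: "For study participants with POS, descriptive statistics for percent change from Baseline (as defined in Section 3.2.14) in 28-day seizure frequency will be presented". Sections 10.1.3 and 10.1.4 count participants with reductions of at least 50% and 75%, which Section 3.2.15 measures against Baseline.

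Section 3.2.20 defines the percentage of seizure-free days and states: "The change in percentage of seizure-free days will be calculated relative to Baseline". No analysis in Section 10 takes this measure up.

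**The concern.** One stated objective (Section 2.1) is preliminary efficacy data on seizure frequency over long-term exposure. With no control arm, the natural reference is the participant's own pre-treatment state. POS participants are compared with it. For the generalized subgroup, the one dedicated seizure variable is not. A reader of the planned table will see a mean or median number of seizure days on treatment and will not be able to tell whether it is lower, the same or higher than before lacosamide.

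The omission is more noticeable because the SAP already defines a Baseline-referenced measure carrying the same information and then assigns it to no table.

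**Working it through.** The SAP states no figure to reproduce. The check compares the definitions and then asks what the planned table could distinguish.

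**1. Seizure days and seizure-free days are complements.** Let D be the diary days on which seizures were assessed, S the seizure days (3.2.16) and F the seizure-free days (3.2.17, 3.2.20). Every assessed day is one or the other, so S + F = D. With P = 100 × F/D:

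- seizure days per 28 = 28 × S/D = 28 × (1 − P/100)
- change in seizure days per 28 = −0.28 × change in P (percentage points)

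A rise of 25 points in P is therefore −0.28 × 25 = −7 seizure days per 28. Tabulating the 3.2.20 change would supply the missing comparison. The 28 × S/D form also has to be written down: 3.2.16 defines only a single seizure day, and the 28/D scaling in 3.2.13 is written for seizure counts.

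**2. What the level alone can show.** The values below are assumed, since the SAP gives none.

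| Treatment-period level per 28 days | Assumed Baseline | Percent change |
|---|---|---|
| 10 | 20 | (10 − 20)/20 = −50% |
| 10 | 7 | (10 − 7)/7 = +43% |
| 6 | 12 | (6 − 12)/12 = −50% |
| 6 | 6 | 0% |
| 6 | 3 | (6 − 3)/3 = +100% |

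The same entry in the planned table fits improvement, no change or worsening.

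**3. Whether another planned output fills the gap.**

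- Historical seizure counts (6.3.3) are summarized by seizure subgroup, but they are numbers of seizures recalled over 4 weeks. Without day information they cannot be converted to seizure days.
- Seizure-free status (3.2.18, 10.1.6) is assessed on treatment and does not register partial improvement.
- The optional splits in 2.3.4.3 by interval or visit could show a trend on treatment, but they add no Baseline.
- The Clinical and Caregiver Global Impressions (10.2) are relative to Baseline but combine seizures, adverse events and function in one rating. PedsQL change (10.3) measures quality of life.

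**4. Whether a diary Baseline exists for this subgroup.** Direct enrollers are described as having partial-onset seizures (2.4.1.2), and 3.2.12 puts a participant from outside SP0966 who reports any Type I seizure in the POS group. The generalized subgroup is therefore essentially rollovers. For rollovers, 3.3 takes Baseline from before the first lacosamide dose in the original study. Section 10.1 says Baseline seizures draw on the historical count and on "the seizure diary data collected from the date of the Screening Visit to the day prior to the date of first dose of LCM", without limiting this to one enrolment route, but 3.3 ties that diary to direct enrollers. The SAP does not state that SP0966 or EP0060 kept a daily diary before the first dose.

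**5. Limits of a short Baseline.** With 3 assessed days, 28 × S/3 can only be 0, 9.3, 18.7 or 28. With a Baseline of 0, percent change is undefined.

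**The case against.** The strongest reply is that 10.1.5 does what the variable's name asks. In 2.3.4.2 the POS variable is named as a percent change from Baseline and the generalized one as a plain rate, and the SAP's own amendment history attributes the efficacy variables to Protocol Amendment 8. This stands in part: there is no contradiction or error between the two sections. The point is that the chosen summary serves the objective poorly.

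Second, the necessary diaries may not exist. This stands. A reader might infer from 3.2.20 that pre-dose diaries are already required for these participants. The text does not support that: 3.2.20 is a general definition that direct enrollers' diaries alone could satisfy. EP0060 lasts about 1 to 5 days, and its RxL group was already taking oral lacosamide.

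Third, a reader might infer that generalized-seizure participants have no Baseline-referenced outcome at all. That goes too far. Under Section 10 the Global Impressions and PedsQL change are repeated by seizure subgroup where applicable, historical counts are summarized by subgroup, and any derived change would appear in listings (3.1). None of these is a summarized quantitative measure of change in seizures.

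Fourth, Section 4.2.5 says efficacy is not the primary objective and that the setting is uncontrolled, with individualized dosing of lacosamide and other AEDs. That limits the importance of the point but does not make the level interpretable.

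**Conclusion.** The point holds in a conditional form. As planned, the dedicated secondary variable for generalized-seizure participants cannot show direction of change, and the Baseline-referenced complement in 3.2.20 reaches no Section 10 summary. The figures in the table above are illustrative; the logic does not depend on them.

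The size is moderate. One secondary descriptive variable in one subgroup is affected; no hypothesis test, primary variable or safety conclusion is. How far it can be repaired rests on an assumption the SAP does not settle: that the parent studies recorded daily seizure diaries before the first dose. If they did so for only some participants, the change summary covers only those. If for none, the remedy is a plain statement of what the level cannot show.

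**What to change.** Amend Section 10.1.5 as follows:

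1. Define seizure days per 28 days as 28 × seizure days / assessed diary days, for Baseline and for the Treatment Period.
2. For generalized-seizure participants with a daily diary before the first dose in the original study, summarize Baseline, treatment-period value and absolute change. Tabulating the 3.2.20 change in percentage of seizure-free days would be equivalent.
3. Give percent change only where Baseline is above 0, and state a minimum number of assessed Baseline diary days.
4. Report how many participants have and how many lack such a Baseline.
5. State that the recalled 4-week count is not used for this variable.
6. If the parent studies hold no pre-dose daily diary, say in the SAP and the report that the treatment-period level cannot be read as improvement or worsening.

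The cost is a short change to the SAP wording and one or two extra columns or tables, with no new data collection where the diaries exist. Someone must first check what SP0966 and the other parent studies recorded. The downside is that the change columns may describe only part of the subgroup, which is why the counts in step 4 are needed.

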### 10.1.6 Seizure-free status

The number and percentage of study participants achieving a seizure-free status (as defined in Section 3.2.18) will be presented for overall treatment period. This will be presented by completer cohorts (as defined in Section 3.2.19).

The number and percentage of study participants seizure-free among completer cohorts (as defined in Section 3.2.19) will also be presented separately by seizure type (simple partial, complex partial, secondarily generalized) for subjects with POS.

Seizure-free status will also be presented by seizure time intervals (as defined in Section 3.2.21). The number and percentage of study participants with seizure-free status at the end of each time interval during the treatment period will be presented separately by seizure type (simple partial, complex partial, secondarily generalized) for POS.

## 10.2 Global Impression of Change

### 10.2.1 Clinical Global Impression of Change

The Clinical Global Impression of Change is a 7-point categorical rating scale in which the investigator should provide his/her assessment of the subject's clinical status, compared to Baseline, including an evaluation of seizure frequency and intensity, the occurrence of AEs, and subject's functional status. This will be assessed at least once per year and will be completed according to the tabular schedule of study procedures.

The number and percentage of study participants by Clinical Global Impression of Change value will be summarized by visit and Last Visit. The denominator for the percentage calculation will be based on the number of study participants with non-missing values. In addition, the 3 improvement values (Very much improved, Much improved, and Minimally improved) grouped as "Improved" and the 3 worsening values (Minimally worse, Much worse, and Very much worse) grouped as "Worsened", together with the "No change" group will be summarized by visit and Last Visit and grouped by modal daily LCM dose, using the levels defined in Section 3.2.8. The denominator for the percentage calculation will be based on the number of study participants with non-missing values.

Clinical Global Impression of Change data will be listed.

### 10.2.2 Caregiver Global Impression of Change

The Caregiver Global Impression of Change is a 7-point categorical rating scale in which the caregiver (including parent/legal guardian) should provide his/her assessment of the subject's clinical status, compared to Baseline, including an evaluation of seizure frequency and intensity, the occurrence of AEs, and subject's functional status. This will be assessed at least once per year and will be completed according to the tabular schedule of study procedures.

The number and percentage of study participants by Caregiver Global Impression of Change value will be summarized by visit and Last Visit. The denominator for the percentage calculation will be based on the number of study participants with non-missing values. In addition, the 3 improvement values (Very much improved, Much improved, and Minimally improved) grouped as "Improved" and the 3 worsening values (Minimally worse, Much worse, and Very much worse) grouped as "Worsened", together with the "No change" group will be summarized by visit and Last Visit and grouped by modal daily LCM dose, using the levels defined in Section

3.2.8. The denominator for the percentage calculation will be based on the number of study participants with non-missing values.

Caregiver Global Impression of Change data will be listed.

### **10.3 Pediatric Quality of Life Inventory (PedsQL)**

The PedsQL is a validated instrument that consists of generic core scales suitable for use with pediatric populations, including those with acute or chronic health conditions. The PedsQL will be completed up to two times per year and will be assessed according to the tabular schedule of study procedures. The Section 3.2.22 details how the scores for the core domains are calculated.

#### **10.3.1 Pediatric Quality of Life Inventory Ages for $\leq 24$ Months**

The multidimensional PedsQL  $\leq 24$  months generic core scales encompass the following core domains for pediatric HRQoL measurement: Physical Functioning, Physical Symptoms, Emotional Functioning, Social Functioning, and Cognitive Functioning.

Calculated values and changes from Baseline for the total scale score (all items), the psychosocial health summary score, the physical health summary score and each of the 5 scale scores will be summarized for each visit and for Last Visit. All changes from baseline will only be calculated for visits when the subject uses the same form of the questionnaire as administered at baseline.

All PedsQL  $\leq 24$  months data will be listed.

#### **10.3.2 Pediatric Quality of Life Inventory Ages $> 2$ years**

The multidimensional PedsQL  $> 2$  years generic core scales encompass the following core domains for pediatric HRQoL measurement: Physical Functioning, Emotional Functioning, Social Functioning, and School Functioning.

Calculated values and changes from Baseline for the total scale score (all items), the psychosocial health summary score, the physical health summary score and each of the 4 scale scores will be summarized for each visit and for Last Visit. All changes from baseline will only be calculated for visits when the subject uses the same form of the questionnaire as administered at baseline. All PedsQL  $> 2$  years data will be listed.

### **10.4 Health care resource use**

For health care resource use parameters, the following will be evaluated: concomitant medical procedures, health care provider consultations not foreseen by the protocol, and hospitalization/ER visits. Health care resource use parameters will be collected according to the tabular schedule of study procedures. Summaries will be presented during the Treatment Period.

#### **10.4.1 Healthcare provider consultations**

The number of healthcare provider consultations per subject for the Treatment Period will be summarized. The number of healthcare provider consultations will be summarized using the categories 0, 1, 2, 3, 4, and 5 or more.

The number of healthcare provider consultations during the Treatment Period will be summarized by type of provider (General Practitioner, Specialist Physician, Nurse, or Other).

Percentages will be relative to the number of healthcare provider consultations during the Treatment Period.

All healthcare provider consultations data will be listed.

#### **10.4.2 Hospital stays and ER visits**

The number of hospital stays per subject during the Treatment Period will be summarized. The number of hospital stays will be summarized using the categories 0, 1, 2, 3, 4, and 5 or more. The number and percentage of study participants with specific reasons for duration of hospital stays will be summarized for the duration of the Treatment Period.

The durations of hospital stays for the Treatment Period will be summarized. Duration of hospital stays (as defined in Section 3.2.23) will be categorized as 0 days, 1-5 days, 6-10 days, 11-15 days, and >15 days, and summarized for the duration of the Treatment Period.

An event logged on the Hospitalization/ER Visit CRF/eCRF module where ER is marked as initial entry point will be defined as an ER visit. An ER visit with a subject transfer to an inpatient general ward will also be counted as a hospitalization. However, all other instances of ER visits (where subject transfer is not to an inpatient general ward) will not be counted as hospitalizations. Descriptive statistics for the number of ER stays during the Treatment Period will be presented. The number of ER visits will be summarized using the categories 0, 1, 2, and 3 or more. The number and percentage of study participants with specific reasons for duration of ER visits will be summarized for the duration of the Treatment Period.

Hospitalizations with either a partial admission or discharge date are ignored for the calculation of duration of hospital stay. However, such hospitalizations are counted for the number of hospital stays. Study participants with no hospital stays will have a duration of 0 days. Should distinct records for hospital stays overlap, then the days during the overlap will only be counted once. Similarly this also applies for ER visits.

All hospitalization and ER data will be listed.

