#### Treatment Period

This is defined as the period of time from the date of first dose of LCM in SP848 to the latter of the last LCM dose date and the study Termination Visit (ie, Early Termination Visit) date.

The Treatment Period is further broken down into the Titration Period and the Post-Titration Period for direct enrollers:

- Titration Period: defined as the date of the first dose of study medication to the day prior to date of Visit 1 or the date of Early Termination (ET) visit in the situation where a subject discontinues prior to the last visit in the Titration Period.
- Post-Titration Period: defined as the date of Visit 1 to the end of the Treatment Period.

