### **3.2.3 Mapping of assessments performed at Early Termination Visit**

Safety and efficacy assessments at an Early Termination Visit (ETV) that correspond to a scheduled visit will be summarized at the scheduled visit corresponding to the ETV if the assessment was scheduled to occur at that visit. Such assessments will also be considered for Last Visit. Study participants who prematurely discontinue the study will be evaluated based on the data collected at each visit attended. For those study participants the ETV will be mapped to the next scheduled visit, ie, the assessments documented at Visit 13/ETV will be assigned to the next scheduled visit, for which the corresponding assessment is scheduled, following the last documented visit.

In particular, assessments which are done at all visits during the Treatment Period (eg, vital signs, body weight and height), will have ETVs corresponding to a scheduled visit mapped to the corresponding scheduled visit.

For study participants enrolled from sites in Japan, they are allowed to stay in the study longer than 2 years. Such study participants will have a separate ETV if they are in the study after Visit 13.

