#### **3.5.3 Full Analysis Set**

The Full Analysis Set (FAS) will be used for the analysis of seizure data and will consist of all study participants in the SS, who have at least 1 completed post-Baseline seizure diary.

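### Consultations, hospital stays and ER visits are summarized only as counts over Treatment Periods of unequal length, so the columns cannot be compared without a rate per subject-year

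*SAP*

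**What the plan says.** Section 10.4 sets one time basis for all health care resource use: "Summaries will be presented during the Treatment Period". Within it:

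- Consultations (10.4.1): "The number of healthcare provider consultations per subject for the Treatment Period will be summarized", banded 0 to 5 or more.
- Hospital stays (10.4.2): "The number of hospital stays per subject during the Treatment Period will be summarized", banded 0 to 5 or more. Stay durations are banded from 0 days to more than 15 days, and participants without a stay are assigned 0 days.
- ER visits (10.4.2): "Descriptive statistics for the number of ER stays during the Treatment Period will be presented", banded 0 to 3 or more.

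The Treatment Period definition in Section 3.2.2 reads, in part: "the period of time from the date of first dose of LCM in SP848 to the latter of the last LCM dose date". A termination visit after that date extends it. Its length is therefore individual. Section 2.4.1.2 allows direct enrollers up to 2 years. Section 3.2.3 says of participants at sites in Japan that "they are allowed to stay in the study longer than 2 years". The exposure bands in 3.2.7 run to above 48 months. Entry to the Full Analysis Set (3.5.3) requires only participants of the Safety Set "who have at least 1 completed post-Baseline seizure diary", with no minimum time on treatment.

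Results are shown overall and by seizure classification subgroup (Section 10), and by age group under the default in Section 3.1.

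**The concern.** A child who leaves after a month without an admission falls in the same zero category as a child observed for years without one. A count without its observation time does not show how intensively care was used.

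This matters most when columns are set side by side. Under 2.4.1.2, direct enrollers must be at least 4 years old with partial-onset seizures. They therefore fall in the age columns from 4 years up and, by the rules in 3.2.12, should fall in the partial-onset column. The column below 4 years holds rollover participants only. Enrollment route, and with it permitted follow-up, is thus partly tied to the displayed subgroups. A difference between columns may reflect use of care, time observed, or both, and the planned tables cannot separate them.

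The SAP allows for time elsewhere: seizures are standardized to 28 days (3.2.13), adverse events are shown by time interval (8.2) and subject-years are derived (3.2.7). It does neither for resource use.

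**Working it through.** The SAP states no rate or sample-size figure for these variables, so there is nothing to reproduce. The event rates, dropout pattern and follow-up distributions below are assumptions.

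**1. Range of follow-up.** By 3.2.5 and 3.2.7 a month is 28 days. The top band starts at 48 × 28 = 1,344 days, and 1,344 / 365.25 = 3.68 years. It has no upper limit. There is no stated lower limit; very short follow-up is an inference from that absence.

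**2. Dependence of the count on follow-up.** With a constant rate r per year over T years, the expected count is rT and, under a Poisson model, P(at least one event) = 1 − exp(−rT).

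| Assumed rate per year | 168 days | 672 days | 1,344 days |
|---|---|---|---|
| 0.1 | 4.5% | 16.8% | 30.8% |
| 0.5 | 20.5% | 60.1% | 84.1% |
| 1 | 36.9% | 84.1% | 97.5% |

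For example, 0.5 × 168 / 365.25 = 0.230 and 1 − exp(−0.230) = 20.5%. Within a row, use of care is the same and only follow-up differs.

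**3. Effect of early dropout.** Assume 0.3 stays per year throughout.

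- All followed 2 years: mean 0.3 × 2 = 0.60; zero stays exp(−0.6) = 54.9%.
- 40% leave uniformly during year 1, the rest followed 2 years: mean follow-up 0.4 × 0.5 + 0.6 × 2 = 1.40 years; mean count 0.3 × 1.40 = 0.42; zero stays 0.4 × (1 − exp(−0.3)) / 0.3 + 0.6 × exp(−0.6) = 0.346 + 0.329 = 67.5%.

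The mean is 30% lower (0.42 / 0.60 = 0.70) and the zero category 12.6 points higher, with no difference in use.

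**4. Share of the variation due to follow-up.** Share = r²Var(T) / [rE(T) + r²kE(T²) + r²Var(T)], where k is the squared coefficient of variation of individual rates. For T uniform on 28 to 1,344 days, E(T) = 686 / 365.25 = 1.878 years, Var(T) = (1,316 / 365.25)² / 12 = 1.082 and E(T²) = 1.082 + 1.878² = 4.609.

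- r = 0.3, k = 0: 0.0974 / (0.5634 + 0.0974) = 15%.
- r = 0.3, k = 1: 0.0974 / (0.5634 + 0.4148 + 0.0974) = 9%.
- r from 0.1 to 5: 5% to 74% with k = 0; 4% to 18% with k = 1 or 2.
- T uniform on 28 to 731 days, same rates: 3% to 60% with k = 0; 2% to 16% with k = 1 or 2.

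**5. The rate.** In step 3, 0.60 / 2 = 0.30 and 0.42 / 1.40 = 0.30, so both groups give the same rate. This follows by construction, because the example assumes a constant rate and dropout unrelated to use.

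**The case against.** The best defence is that the denominator is already planned. Section 8.1 presents exposure duration and subject-years by seizure classification subgroup and for the Full Analysis Set, and 3.1 adds the age groups. Where a mean count is tabulated, a reader can divide it by mean exposure, column by column. This stands in part. It gives an approximate mean rate, because exposure under 3.2.7 ends at the last dose while the Treatment Period may run on to a later termination visit. It does not correct the banded percentages or the zero category.

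It is also true that resource use is among the other efficacy variables (2.3.4.3), that the study is descriptive without testing, that no formal subgroup comparison is planned and that all the data are listed. This limits the priority. It does not make an unadjusted percentage comparable between columns. Consultations by type of provider are outside the point, since those percentages use consultations as denominator.

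A rate has limits of its own. If care is used mainly early in treatment, or if heavier users leave sooner, a pooled rate also moves with the follow-up mix. For the same reason the direction of the distortion cannot be stated in advance.

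**Conclusion.** The point holds as one of confounding. Counts, duration bands and zero-event percentages in 10.4.1 and 10.4.2 depend on how long each participant was observed and cannot be read across the age and seizure-classification columns. The size cannot be derived from the SAP. The shift from 54.9% to 67.5% with no stay is an illustration that rests on an assumed 0.3 stays per year and an assumed 40% leaving in year 1.

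A reader might infer that the counts mainly measure length of follow-up. The documents do not support that. At 0.3 stays per year, follow-up explains about 15% of the variance with equal rates and less if rates vary between children. In the settings tried it passes one half only if all children share the same rate, of about 2 per year or more over the wide range of follow-up or 5 per year over two years.

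A reader might also contrast an early-dropout group with one followed 4 years throughout (1.20 / 0.42, or 2.9-fold at 0.3 per year). No planned column is stated to have such follow-up, and Section 10.4 plans no split by Japan or by enrollment route.

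**What to change.** In 10.4.1 and 10.4.2, for each displayed column and for consultations, hospital stays, hospital days and ER visits, add total events (or days) in the Treatment Period divided by total Treatment Period subject-years. Print the subject-years beside the rate. Take the denominator from the 3.2.2 period, not from the dose-to-dose exposure in 3.2.7, so that events and time cover the same days. Note under the hospital-day rate that stays with partial dates count as stays but add no days, as 10.4.2 already provides.

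State that any reading across subgroups uses the rate and that the count bands are supportive. Add that the rate removes the dependence on follow-up only so far as use is roughly constant over time and dropout is unrelated to use.

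The cost is one further line per table from dates already held, with a little more programming. No new data are needed.
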